7.7 Preparation and labelling of Non Investigational Medicinal Product

Not applicable

7.8 Drug accountability

Not applicable

8. METHODS

8.1 Study parameters/endpoints

8.1.1 Main study parameter/endpoint

To investigate the modifying effects of WHO-recommended sodium intake (90 mmol per day) vs. high sodium intake (targeted at 250 mmol per day) on the effect of ertugliflozin 15 mg daily, versus placebo, on 24-hour blood pressure in overweight/obese adults with type 2 diabetes.

8.1.2 Secondary study parameters/endpoints (if applicable)

To investigate the efficacy of ertugliflozin 15 mg daily, versus placebo, in overweight/obese adults with type 2 diabetes to reduce the hypertensive effects of a high-sodium diet (250 mmol per day) versus 24-hour blood pressure measurement during participant's normal diet (170 mmol/per day) obtained at screening.

8.1.3 Other study parameters (if applicable)

To investigate the modifying effects of WHO-recommended sodium intake (90 mmol per day) vs. high sodium intake (targeted at 250 mmol per day) on the effect of ertugliflozin 15 mg daily, versus placebo, on the following parameters in overweight/obese adults with type 2 diabetes:

- GFR by iohexol clearance
- Hematocrit
- Office blood pressure
- Kidney oxygenation
- Parameters of intra kidney hemodynamic function including ERPF by p-aminohippurate (PAH) clearance and renal vascular resistance
- Body anthropometrics
- Fasting plasma glucose
- Albumin excretion rate (24 hour)
- 24-hr urinary glucose excretion
- Urinary and plasma biomarkers

8.2 Randomisation, blinding and treatment allocation

The study is blinded with ertugliflozin and matching placebo's being provided by MSD. The investigator will send a computer-generated randomization list (block randomization of 4) via an automated system (Castor EDC) to the trial pharmacy of Amsterdam UMC. In this way, all study participants and trial personnel remain blinded at all times. Unblinding will only occur in a medical emergency. The sodium diets are

of course open label. Each participant receives sufficient tablets (ertugliflozin or matching placebo) for each treatment period of n=10 days.

8.3 Study procedures

Recruitment

Potential participants will be recruited by researcher physicians involved in this trial using methods that are established practice for all human studies in the Diabetes Center Amsterdam UMC-VUMC:

- 1) Via advertisements in (local) newspapers
- 2) Use of a Diabetes Center database to approach volunteers from previous studies, who have given written informed consent to be available for future studies
- 3) Through the Diabetes Center website (www.diabetescentrum.nl)
- 4) Via general practitioner offices with whom we have collaborations.,

Potential participants will be approached by the general practitioner

- 5) Where possible, subjects will be recruited from the out-patient clinic of the Diabetes Center / Department of Internal Medicine Amsterdam UMC-VUmc or affiliated hospitals / pharmacies

- 6) Online advertising directed at patient support groups

In case of a positive response, the information letter and informed consent forms will be sent to these individuals. They will then be contacted by telephone by the research physician to answer any remaining questions and make an appointment for a screening visit if the individual wants to participate.

Screening and eligibility (V1 and T1)

After giving extensive oral and written information, and sufficient time to consider study participation (minimally one week), a written informed consent form will be obtained from the subjects before screening. Once the participant signs the informed consent form he/she will be assigned a unique study number, which will be used for identification.

The screening procedure will consist of obtaining an extensive medical history (including disease history, current medical conditions and use of medication, substance use, employment, education, family history), complete physical examination, drawing blood for hematologic and biochemistry testing (full blood count, glucose, HbA1c, creatinine, ALT, AST, gamma-glutamyl transferase (GGT), creatinine, albumin, and thyroid-stimulating hormone (TSH)), urine screening, urine creatinine and albumin, and a 12-lead electrocardiogram (ECG). If subjects are eligible, the investigator will inform them within two weeks after screening. Then, 24-hour urine and 24-hour blood pressure are obtained in order to be able to study hypothesis 2 (effect of ertugliflozin on sodium sensitivity).

After confirmation of eligibility during screening, a 24-hr blood pressure measurement as well 24-hr sodium excretion is measured prior to the dietary blocks as detailed below. This 24-hr sodium and blood pressure measurement will be crucial for hypothesis 2. Urine containers and 24-hr blood pressure meters are provided to the patient and collected after recording.

Screening	Day 0	Day 1 (offered at home of participants to reduce travel)
Medical history	X	
Physical examination	X	
Review of medication	X	
Office blood pressure	X	
Routine hematology and chemistry	X	
HbA1c	X	
Urinary dipstick	X	
Start 24-hr urine sodium collection	X	
Start 24-hr BP measurement	X	
Return 24-hr urine sodium collection		X
Return 24-hr BP measurement		X

Subsequently, 4 of the blocks of 20 days below are conducted in random order with differences in study medication (placebo versus ertugliflozin) and sodium diet (90 mmol/day versus 250 mmol/day). The washout is 4 weeks between the blocks. Please refer to the figure on page 11. Urine containers are provided to the patients.

A sodium diet is commenced (either aimed at 90 mmol/day or 250 mmol/day) and it is expected that after 10 days this is reached (+/- 20%, due to normal variation in sodium excretion). This will be assessed with two 24 hour urine collections. Subsequently, the diet is continued and treatment with the study medication commences. In the morning of day 9, 24-hour blood pressure recording starts. At the study visit at day 10 of treatment, endpoints are collected following an overnight fast of 10-hours at our clinical trial unit as indicated below. A flow chart of study activities is attached below.

Subject will arrive at Amsterdam UMC location AMC for multimetric MRI following an overnight fast. Subjects are then brought to Clinical Research Unit (CRU) location VUMC where the 24-hour urine collection is processed (in order to assess sodium

excretion and other variables of interest obtained from 24-hr urine collection). The 24-hour blood pressure recording is stopped. Two intravenous catheters will be placed in both forearms for blood sampling and for the administration of test-agents (e.g. iohexol and PAH). A total of 125 mL blood will be drawn during the day for this purpose. The renal protocol commences with measurement of GFR and effective renal plasma flow (ERPF) based on continuous infusion for 2.5.

During the infusion, several measurements will be performed including anthropometrics, bio-impedance analysis, blood pressure measurement and collection of samples for biomarker analysis.

	Day -10	Day -2	Day -1	Day 0	Day 3	Day 10
Start sodium-diet (continue until day 10)	X					
24-hr urine sodium (compliance)		X	X			
Start study medication (continue until day 10)				X		
Telephone call compliance					X	
Recent history						X
24-hr blood pressure						X
Measured GFR						X
ERPF						X
Intrarenal hemodynamic function						X
Office blood pressure						X
Hematocrit						X
Renal oxygenation (BOLD MRI)						X
RAAS components						X
Collection of biomarkers						X
Body anthropometrics						X
24-hr urine analysis (sodium, UACR)						X

Efficacy measurement more detailed:

- 1) **Height.** A height measuring board will be used to assess height. Patients will be asked to remove their footwear and headgear and to stand on the board with their feet together, heels against the back board and knees straight. The patient should be looking straight ahead, without tilting the head up, with eyes and ears at the same level. The measure arm will gently be moved down onto the head of the participant and height will be read in centimeters at the exact point.
- 2) **Weight.** Body weight will be recorded by a digital calibrated weighing scale on a firm, flat surface. Patient will be asked to remove their footwear, extra layers of clothing, jewelry and any items in his/her pockets before standing still on the weighing scale with arms placed on the side. Measurement will be recorded on the Case Report Form (CRF) to the nearest kilogram. No deduction for clothing will be permitted.
- 3) **Body Mass Index (BMI).** BMI will be derived from height and bodyweight by using the mathematical formula: $BMI = [kg/[m]^2]$.
- 4) **Waist circumference.** A constant tension tape will assess waist circumference with the patient in a standing position with the arms relaxed at the sides and without clothing, that is, directly over the skin. Measurement will be performed at the midpoint between the lower margin of the last palpable rib and the top of the iliac crest at the end of a normal expiration.
- 5) **Body-impedance analysis.** To measure body fat content we will use the tetrapolar Soft Tissue Analyzer® (STA, Akern, Florence, Italy), which can perform Bio-Impedance Analysis (BIA). This technique measures the resistance in the body tissues when a 50 kHz AC electrical current is given between four electrodes. Resistance can be measured by placing two electrodes on the dorsal hand and two on the foot at the unilateral side of the body (Lukaski & Bolonchuk, 1988). Extracellular water (ECW) as a percentage of total body water (TBW) and body cell mass (BCM) will be calculated independent of weight and height.
- 6) **ECG:** A 12-leads ECG will be made in the fasting resting state during screening in order to assess cardiac conduction parameters. Heart rate on the ECG will be defined as the mean rate of 10 R-R intervals. PQ-time, QRS-time and QT-time will be calculated, QT-time will be corrected for heart rate by using the Bazett formula (C. Bazett, 2006). The cardiac vector and ECG morphology will be assessed.
- 7) **Blood pressure and heart rate (office):** Blood pressure and heart rate will be measured using an automatic oscillometric device (Dinamap®, GE Healthcare) After an acclimatization period of >5 minutes, blood pressure will be measured three times at the non-dominant arm, with the subject in a semi-recumbent position, using an appropriate cuff-size. The mean of the last 2 measurements will be used as final value (Mengden et al., 2010; Pickering et al., 2005).
- 8) **GFR** is measured by steady-state plasma iothexol concentrations measured at T=120 and T=150 as done in our previous approved protocols.

9) **ERPF** is measured by steady-state plasma PAH concentrations measured at T=120 and T=150 as done in our previous approved protocols.

10) **Filtration fraction** (GFR/ERPF) and renal vascular resistance (ERPF/mean arterial pressure) are calculated.

12) **24-hour blood pressure** is derived from Mobil-O-graph devices (24 ambulatory blood pressure monitors, The Netherlands), which will be available at both sites.

Daytime systolic blood pressure (SBP), daytime diastolic blood pressure (DBP), nighttime SBP, daytime DBP and nocturnal dipping pattern (in mmHg) are recorded.

12) sodium sensitivity is calculated as following: changes in blood pressure due to the high-sodium diet versus diet at screening (estimated based on experience/previous trials at ~165-170 mmol/day) and the effect on this parameter by ertugliflozin versus placebo.

13) **Multiparametric MRI** will be carried out to measure additional kidney physiology parameters. The multiparametric MRI is performed on a tesla 3 machine. The MR examination will last 45 minutes maximum. During the scans, heart rate and blood pressure will be monitored. Patients get hearing protection in the form of ear-plugs and headphones. During the examination, they are in contact with the technicians via the intercom. Throughout the examination, patients will receive breathing instructions, for example to hold their breath for 20 seconds maximum, in order to produce accurate images. The MRI exam includes BOLD MRI to measure oxygenation, but also ASL and phase contrast MRI to obtain renal artery blood flow.

- BOLD-MRI: BOLD-MRI will be performed in order to measure renal tissue oxygenation. BOLD MRI exploits the difference in magnetic properties between oxygenated and deoxygenated hemoglobin (Prujm et al., 2018). Presence of deoxygenated hemoglobin will result in an accelerated signal decay on the BOLD images. Measurement of this signal decay results in a measure of the amount of deoxygenated hemoglobin, the apparent relaxation rate $R2^*$, which inversely relates to level of tissue oxygenation.

-ASL: In ASL, the blood travelling through the aorta is magnetically labeled before acquiring an image (the "label" image) (Odudu et al., 2018). Other images are acquired without any label (the "control" image). The difference between the label and control image will only be around 2%, so this procedure is repeated several times. The average difference between those images can be used to obtain a perfusion map of the kidney. Phase-contrast MRI is done to obtain renal artery blood flow.

14) **serum biomarkers**: hematocrit, serum albumin, plasma glucose and additional serum biomarkers are measured in the fasted state

15) **24-hour urine albumin and glucose excretion** is measured. Additional material for urinary biomarkers of interest such as markers of inflammation and electrolytes is stored.

16) **Safety and tolerability**: recent history and focused physical examination is carried out to assess potential adverse effects of study medication.

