There is no clear health benefit for the study participants, except that participation will provide insight into their sodium intake and knowledge how to reduce sodium intake to WHO-recommended amounts, which may benefit their long-term health. The short-term treatment with SGLT2 inhibitor ertugliflozin will not provide lasting benefits. On the other hand, the drug has little side effects, especially during short-term treatment, which will be closely monitored. The most commonly observed side effect (usually after more prolonged treatment) involves genital mycotic infections, which can easily be treated with antifungal topicals. Glucose levels and blood pressure are lowered during treatment. There are no health risks to short-term changes in sodium diet. Potential changes in blood pressure during the high-sodium diet are closely monitored. The study procedures are safe. There are no risks with undergoing MRI procedures and the use of iohexol and PAH to measure kidney hemodynamic function bears no risk, with >1500 tests carried out in our department. Burden of participants includes 5 visits (including screening); 4 visits where an MRI scan (duration 30 min) is performed and where 2 intravenous catheters are placed for tracer infusion during 2,5 hours; 13 24-hr urine collections and 5 24-hr blood pressure collections. A total of maximally 500 mL blood will be withdrawn over the course of a number of months. The study team will mitigate travel for the participants by collecting 24-hr blood pressure and 24-urine samples at home.

INTRODUCTION AND RATIONALE

Diabetic kidney disease (DKD) remains the leading cause of chronic kidney disease (CKD) and dialysis in the developed world, and a major cause of premature mortality. Sodium-glucose cotransporter 2 (SGLT2) inhibitors confer cardiovascular and renal protection in many, but not all people with type 2 diabetes (T2D) (1). Yet, the mechanisms of these salutary cardiorenal benefits remain unclear, and are incompletely explained by the modest improvements in blood pressure, glycemic control, body weight, and serum uric acid (2). A better understanding of the mechanism of cardio-renal protection in response to SGLT2 inhibition is therefore needed to determine which patients would see the greatest benefit from this drug class and also how to augment the beneficial effects with complimentary drugs and/or lifestyle changes such as changes in dietary sodium intake.

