3. STUDY DESIGN

The study is a bi-center randomized, placebo-controlled, crossover intervention study. Total number of included participants is 34, which undergo 4 conditions in randomized order (randomization list generated by computer and supervised by pharmacy; blinded to investigator). While the treatment will be blinded for all participants, the sodium interventions are open-label. Study design is shown in the figure below.

The 4 conditions are:

- 1) low-sodium diet; placebo
- 2) low-sodium diet; ertugliflozin 15 once daily
- 3) high-sodium diet; placebo
- 4) high-sodium diet; ertugliflozin 15 mg once daily

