10.3 Other study parameters

All exploratory variables are analysed as described under 10.1. For exploratory parameters, no correction for multiple testing will be conducted and the exploratory nature of the data will be stressed when the data are reported in a manuscript as our group has done previously.

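### Body weight, an exploratory measure, is recorded only to the nearest kilogram from a digital calibrated scale, which adds small, avoidable random error to weight and BMI contrasts

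*Combined protocol and SAP*

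**What the plan says.** Section 8.3, item 2, specifies the instrument: "Body weight will be recorded by a digital calibrated weighing scale on a firm, flat surface". It standardises the weighing by having shoes, outer layers, jewellery and pocket contents removed, and allows no correction for the clothing that remains. It then sets the recording rule: "Measurement will be recorded on the Case Report Form (CRF) to the nearest kilogram". No reason is given for whole kilograms, and the scale's display resolution is not stated. Item 3 makes BMI depend on the same figure: "BMI will be derived from height and bodyweight by using the mathematical formula".

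Weight enters the analysis through section 8.1.3, which lists "Body anthropometrics" among the exploratory parameters. The flow chart in section 8.3 places it at day 10 of each block. Section 10.3 says: "All exploratory variables are analysed as described under 10.1". Section 10.1 sets out an analysis with diet and treatment main effects and their interaction.

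On design, section 3 says: "Total number of included participants is 34, which undergo 4 conditions in randomized order". Section 8.2 gives the drug exposure: "Each participant receives sufficient tablets (ertugliflozin or matching placebo) for each treatment period of n=10 days". The only indication of the size of the weight effect is in the introduction, which attributes to the drug class "modest improvements in blood pressure, glycemic control, body weight, and serum uric acid", with no figure in kilograms.

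**The concern.** The protocol takes care over the weighing and then, if the scale reads finer than 1 kg, discards the decimal. Each rounded value carries its own error of up to half a kilogram. The interaction contrast for a participant combines four such values, so it carries four such errors. Drug exposure is short and the class effect is described only as modest, so precision in within-participant differences is worth having. At stake is some precision for weight and BMI as exploratory measures, in a trial with 34 participants.

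**Working it through.** **The plan's own figure.** The plan gives no power or precision figure for weight. Its one calculation, for 24-hour blood pressure, reproduces: a paired t-test with a difference of 4 mmHg, an SD of 8 mmHg and two-sided alpha of 0.05 gives 79.5% power at n = 33 and 80.8% at n = 34. Weight does not enter that calculation.

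**Inputs**
- Recording resolution: 1 kg (section 8.3, item 2).
- Design: four conditions per participant, 34 participants (section 3).
- Within-participant SD of a single weighing, called s below: not in the documents. Assumed range 0.5 to 2.0 kg.

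**Step 1: rounding error alone.** Treat the error as uniform over ±0.5 kg.
- One reading: 1/√12 = 0.289 kg.
- Difference of two conditions: √(2/12) = 0.408 kg.
- Interaction contrast, four readings: √(4/12) = 0.577 kg.
- Contribution to the standard error with 34 participants: 0.408/√34 = 0.070 kg for a paired difference and 0.577/√34 = 0.099 kg for the interaction.

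**Step 2: relative cost.** A contrast of k equally weighted readings has variance proportional to k(s² + 1/12) with rounding and ks² without. The ratio is 1 + (1/12)/s² for every such contrast. The equivalent loss of participants is 34 × (1 − 1/ratio).

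| Assumed s (kg) | Variance ratio | Variance increase | Equivalent loss out of 34 |
|---|---|---|---|
| 0.5 | 1.333 | 33% | 8.5 |
| 0.8 | 1.130 | 13% | 3.9 |
| 1.0 | 1.083 | 8% | 2.6 |
| 1.5 | 1.037 | 4% | 1.2 |
| 2.0 | 1.021 | 2% | 0.7 |

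**Step 3: where in the range the trial may sit.** Blocks last 20 days with a 4-week washout between them (section 8.3). Consecutive day-10 visits are therefore 20 + 28 = 48 days apart, and the first and last are 3 × 48 = 144 days apart. Drift over those months is part of s. Participants also keep some clothing on, and section 8.3 has anthropometrics taken during the tracer infusion. Clothing, infused volume and bladder filling therefore add variation. All of this makes the upper part of the range plausible, though the documents cannot settle it.

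**Step 4: power, for illustration only.** The effects here are assumed. With a paired-difference SD of 1.0 kg (s = 1.0/√2 = 0.71 kg), rounding lowers the power for a 0.5 kg interaction from 51.7% to 45.7%, and for a 0.5 kg paired difference from 80.8% to 74.5%. With a paired-difference SD of 2.0 kg (s = 1.41 kg), power for a 1.0 kg interaction goes from 51.7% to 50.0%, and for a 1.0 kg paired difference from 80.8% to 79.2%.

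**Step 5: check by simulation.** For true paired SDs of 0.5, 1.0 and 1.5 kg, the SDs after rounding were 0.644, 1.080 and 1.553 kg; the formula gives 0.645, 1.080 and 1.555. A true mean difference of 1.00 kg was recovered as 1.00 kg, so rounding adds spread but no bias.

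**Step 6: effect of the fix.** At 0.1 kg resolution the rounding SD is 0.029 kg per reading, and the variance increase is 0.01/12 divided by s²: 0.33% at s = 0.5 kg and less above that.

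**BMI.** The largest rounding error per weighing is 0.5/height². For assumed heights of 1.90 to 1.60 m this is 0.14 to 0.20 kg/m².

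**The case against.** The best defence is that this is a recording format for one of ten exploratory items, in a study that section 10.1 itself calls hypothesis-generating. It cannot alter the main conclusions, and other sources of variation in the same weighing may be larger than the rounding. That stands, and it is why the severity is the lowest. A 0.1 kg field would also leave clothed weighing during the infusion as it is, so the gain may be only a few per cent of variance.

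A reader might infer more from the rule than the documents support:
- **That the changes sought are about 1 kg, so rounding hides them.** The plan gives no expected change in kilograms for the drug or for the interaction. Group means are in any case recovered without bias.
- **That weight is the trial's read-out of fluid volume.** The plan gives weight no such role. Section 8.3 estimates extracellular water by bio-impedance, calculated independently of weight and height, and the introduction discusses haematocrit in relation to plasma volume. Rounded weight affects neither.
- **That the lost decimal can never be recovered.** The rule governs the CRF. Section 12.1 mentions source documents separately, and these may hold the displayed reading.
- **That the rounding is certainly needless.** This requires a scale that reads finer than 1 kg. That is likely for a digital calibrated device but is not stated.

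None of these limits gives a reason for keeping whole kilograms.

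**Conclusion.** The point holds as a minor one. The recording rule adds random error with an SD of 0.29 kg per reading and 0.58 kg in the interaction contrast. Those figures follow from the 1 kg resolution with rounding error treated as uniform and independent between readings, which the simulation supports for paired differences. The relative loss rests on the assumed within-participant SD: about a third more variance at 0.5 kg, and 2% to 8% at 2.0 to 1.0 kg. A figure from the low end of that SD range should not be quoted alone, because the spacing of visits and the weighing conditions may well put the true SD higher. The loss concerns weight and BMI only. Blood pressure, the secondary endpoint and the sample size are untouched.

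**What to change.** In section 8.3, item 2, and on the CRF, record weight at the resolution that the scale displays, for example 0.1 kg, and state that resolution for both sites. In item 3, derive BMI from that value. If participants have already been weighed under the present rule, check whether source documents hold the displayed reading before accepting the rounded one. The cost is one CRF field format and one sentence in the protocol, with no added visit, procedure or burden for participants. If a scale displays whole kilograms only, the change gains nothing at that site but does no harm.

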While it was previously thought that sodium sensitivity is exclusively driven by differences in renal sodium excretion, in salt-resistant people, sodium may bind non-osmotically in tissues such as endothelial surface layers and the glycocalyx, preventing water retention and hypertension (23). Integrity of the endothelial surface layer is important for vascular dynamics, and glycocalyx injuries have been implicated in the progression of DKD and cardiovascular disease. Interestingly, the SGLT2 inhibitor empagliflozin was shown to decrease tissue sodium content as measured by MRI, which could theoretically reduce non-osmotic sodium storage (24). On the other hand, SGLT2-inhibitor induced improvements in endothelial function could drive opposite effects with improved non-osmotic sodium storage. Currently, the effects of SGLT2 inhibition on sodium sensitivity are unknown, while its effect on sodium sensitivity may become very relevant in people that consume excess sodium. Given the blood pressure lowering effects of SGLT2-inhibitors, that may be driven by improvements in endothelial function, one could hypothesize that SGLT2 reduce sodium sensitivity.

Dietary sodium intake may modulate the effects of SGLT2 on the kidney and beyond through several mechanisms, as excessive sodium intake has kidney hemodynamic effects. As such, high sodium intake has been shown to increase GFR and effective renal plasma flow (ERPF) in normoglycemic individuals, while blood pressure (MAP) increased to a smaller extent. Given that renal vascular resistance = $MAP/ERPF$, this parameter declined. Filtration fraction ($FF=GFR/ERPF$) increased in the overweight individuals, but not in lean persons (25). As people with T2D are almost all overweight or obese and are usually sensitive to the effects of high-sodium intake (26), the renal hemodynamic effects of SGLT2 inhibitors could be off-set by high sodium intake. This could be secondary to impairment of tubuloglomerular feedback as shown recently for ertugliflozin in rodent studies (27). In addition, given the potential beneficial effect of SGLT2 inhibitors on kidney oxygenation, large amounts of filtered sodium could off-set this mechanisms of action.

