4.4 Sample size calculation

Based on previous studies in patients treated with SGLT2 inhibitors, we expect a change in systolic blood pressure of 6-8 mmHg during normal sodium intake (150 mmol/day) (6,7). Based on our hypothesis, this effect is increased on a low-sodium intake and reduced during high-sodium intake.

We expect a difference of 4 mmHg between the placebo-controlled effects of ertugliflozin on a low- versus high-sodium diet, with a conservative SD on this difference of 8 mmHg.

A total of 34 patients completing the study provide 80% power at a two-sided alpha of 0.05, to detect a 4 mmHg difference with the indicated SD of 8 mmHg. Drop-outs will be replaced.

Based on the RED study (7) and DAPASALT(6) study, the power needed to detect changes in GFR and hematocrit are of sufficient magnitude and therefore we expect sufficient power for these parameters as well. **We will include 34 individuals.**

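### Section 8.3 derives renal vascular resistance as ERPF/MAP, the reciprocal of the protocol's own definition, so this exploratory endpoint would change direction if derived as written

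*Combined protocol and SAP*

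**What the plan says.** Two places in the protocol give a formula for renal vascular resistance.

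- Introduction and rationale, on the kidney effects of high sodium intake. ERPF rose, "while blood pressure (MAP) increased to a smaller extent", and the text then concludes: "Given that renal vascular resistance = $MAP/ERPF$, this parameter declined". Here resistance is pressure over flow.
- Section 8.3, item 10, in the detailed list of efficacy measurements: "renal vascular resistance (ERPF/mean arterial pressure) are calculated". Here it is flow over pressure.

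The quantity is a named outcome. Section 8.1.3 lists "Parameters of intra kidney hemodynamic function including ERPF by p-aminohippurate (PAH) clearance and renal vascular resistance" among the other study parameters, and the Summary places the same item under exploratory endpoints. Section 10.3 sets the analysis: "All exploratory variables are analysed as described under 10.1". That means the two-way model with diet, treatment and their interaction. Section 10.1 also allows log transformation where it is needed for normality, but does not require it for any particular variable.

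**The concern.** Item 10 is the instruction a programmer would follow; the Introduction is background. A programmer working from section 8.3 alone would produce a renal vascular conductance and store it under the name of resistance.

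Direction is the scientific content of this variable. The Introduction suggests that high sodium intake could offset the renal haemodynamic effects of SGLT2 inhibition. A reader of the results will want to know whether the renal vessels dilated or constricted under drug, under diet, and under the two together. With the ratio inverted and the label unchanged, each of those readings would be reversed.

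A second consequence is less obvious. A reciprocal is not a linear rescaling, so on the raw scale an additive interaction need not keep its size or its p-value when the ratio is turned over.

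**Working it through.** **1. The plan's own figure.** The documents give no sample size or power figure for renal vascular resistance. The only one is for the primary blood pressure interaction: "A total of 34 patients completing the study provide 80% power at a two-sided alpha of 0.05", for a 4 mmHg difference, "with a conservative SD on this difference of 8 mmHg".

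- Normal approximation, paired: n = ((1.960 + 0.842) × 8/4)² = 31.4, rounded up to 32.
- Noncentral t: power is 79.5% at N = 33 and 80.8% at N = 34.

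So 34 is reproduced as the smallest N that reaches 80%. Neither resistance formula enters this calculation.

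**2. The two formulas side by side.**

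- Introduction: R = MAP/ERPF.
- Section 8.3, item 10: C = ERPF/MAP = 1/R.

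Whenever R falls, C rises, and the reverse. Filtration fraction, in the same item 10 sentence, is GFR/ERPF in both places, so only the resistance formula is inverted.

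**3. The Introduction's scenario under each formula.** Let ERPF rise by a fraction e and MAP by a smaller fraction m. R changes by (1+m)/(1+e) − 1, which is negative for any e > m. C changes by (1+e)/(1+m) − 1, which is positive for any e > m. The documents give no percentages, so the values below are assumed and shown as a range.

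| ERPF | MAP | Change in MAP/ERPF | Change in ERPF/MAP |
|---|---|---|---|
| +5% | +2% | -2.9% | +2.9% |
| +10% | +3% | -6.4% | +6.8% |
| +15% | +5% | -8.7% | +9.5% |

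The opposite signs follow from the algebra and do not depend on the chosen values.

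**4. Levels, for orientation.** Assume MAP 95 mmHg and ERPF 600 mL/min. Then 95/600 = 0.158 and 600/95 = 6.32. If MAP falls 5% to 90.25 with ERPF unchanged, 90.25/600 = 0.150 (-5.0%) and 600/90.25 = 6.65 (+5.3%).

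**5. The interaction.** Assume these cell values of MAP/ERPF, placebo to drug: low sodium 0.160 to 0.150, high sodium 0.150 to 0.140.

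- Raw MAP/ERPF: the drug effect is -0.010 on each diet, so the interaction is 0.
- Raw ERPF/MAP: 6.250 to 6.667 is +0.417, and 6.667 to 7.143 is +0.476, so the interaction (high minus low) is about +0.06. The change of formula alone creates it.
- Log MAP/ERPF: ln(0.150/0.160) = -0.0645 and ln(0.140/0.150) = -0.0690, so the interaction is -0.0045.
- Log ERPF/MAP: +0.0645 and +0.0690, so the interaction is +0.0045.

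Since ln C = −ln R for every observation, a log-scale analysis gives the same magnitude, standard error and p-value under either formula, with the sign reversed.

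**The case against.** The best reply is that this is a slip of the pen with low stakes. The Introduction shows that the authors know the definition and use it correctly, so whoever derives the variable may well do it properly whatever item 10 says. The endpoint is one part of one entry in a list of ten other parameters. Section 10.3 promises that the exploratory nature of such results will be stressed. Blood pressure and ERPF are each measured at the day 10 visit, so a wrong ratio can be recomputed at any time from stored values.

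All of that stands, and it limits the severity. It does not make item 10 correct. Item 10 is a stated derivation rule, and the documents contain nothing that overrides it.

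Three stronger readings are tempting, and the documents do not support them.

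- A reader might infer that the trial will report reversed results. That happens only if item 10 is coded literally and labelled resistance. The documents contain no derivation code, so this cannot be known.
- A reader might count 34 × 4 = 136 planned renal measurements as compromised. The collected data are unaffected; one derived column would be.
- A reader might infer that the test of the interaction is distorted in general, or that power is lost. The change in size and p-value applies only to an untransformed analysis. The documents give no variability for this endpoint, so no effect on power can be stated.

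**Conclusion.** The point holds as an internal contradiction in the definition of an exploratory endpoint, and item 10 is wrong as written by the protocol's own definition. Followed literally, it yields a conductance under the name of resistance, with every effect reversed in sign. The reversal is certain algebraically; the percentages and cell values used to illustrate it are assumptions. On the raw scale the interaction estimate and its p-value can also differ; under the log transformation that section 10.1 permits, they differ in sign only.

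The reach is narrow. The primary and secondary blood pressure endpoints, GFR, ERPF, filtration fraction and the sample size do not depend on this formula. This is a should-fix correction and not a threat to the trial's main conclusions.

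**What to change.** In section 8.3, item 10, replace the formula so that it reads: renal vascular resistance = mean arterial pressure / ERPF, in line with the Introduction and rationale. Make sure the derivation of the analysis variable uses that formula.

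Do this before database lock, which under the blinding provisions in section 6.8 comes before the code is broken. The correction is then plainly prespecified and cannot be taken for a redefinition made after seeing results.

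The cost is one line of text and a check of one derived variable. It needs no new data, visits or participants, and no change to the analysis model.
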